BACKGROUND AND RATIONALE: The best currently available treatment for patients with relapsed or refractory multiple myeloma uses regimens that include novel agents like lenalidomide, thalidomide, and bortezomib but still yield unsatisfactory long term tumor control with median remission duration not more than one year and median survivals ranging between 1 and 3 years in most studies (1). As myeloma progresses, clones emerge that have more tumor suppressor genes silenced by DNA methylation which may lead to resistance towards used therapies, escape from immune attack, and independence from the bone marrow microenvironment (2-6). In contrast to mutations such epigenetic changes can be corrected with aza nucleoside analogues like azacitidine, which inhibits the methylation of newly synthesized DNA by inhibiting DNA methyltransferase (DNMT) (7-9) and has been shown to improve survival in MDS and WHO AML compared to conventional therapy (10). One of the most active current regimens for relapsed/refractory myeloma uses lenalidomide in combination with dexamethasone yielding a response duration of over 11 months and an overall survival of about 30 months (11). In the upfront therapy setting, low dose dexamethasone in combination with lenalidomide appears to yield at least equivalent survival rates but cause less toxicity than conventional dose dexamethasone (12). This regimen (lenalidomide 25mg day 1-21, every 28 days with dexamethasone 40mg weekly) has rapidly been adapted as one of the standard approaches to newly diagnosed and relapsed myeloma patients. By combining this regimen with azacitidine, resistant myeloma clones, which continue to synthesize DNA despite therapy, may become sensitive through reactivation of silenced tumor suppressor genes leading to a deeper and longer response. In vitro, non-toxic single low doses of azacitidine (1 μ M) can reactivate tumor suppressor genes in myeloma cell lines for 3-7 days (unpublished observations). Doses higher than 2-5 μ M, depending on the cell type, can exert immediate toxicity likely related to nucleoside analogue properties of the drug. Pharmacokinetic data in humans suggest that a single dose of 50mg/m ² subcutaneously reaches concentrations that should be sufficient for DNA demethylation but could cause classical nucleoside analogue toxicity in some patients (2.89 μ M +/- 1.35 μ M SD), higher doses like 75mg/m ² reach 4.88 μ M +/- 1.4 μ M SD and thus almost certainly exert classic nucleoside analogue toxic effects (13). In this study we aim to avoid pronounced nucleoside analogue side effects while maximally exploiting DNA demethylating effects of azacitidine. We will therefore assess the safety of combination therapy with azacitidine given at low but increasing doses up to 50mg/m ²	

twice a week, together with standard dose lenalidomide and low dose dexamethasone in relapsed or refractory myeloma patients in a phase I/II study with 10 additional patients enrolled at the highest tolerated low azacitidine dose to obtain an initial impression of efficacy and to evaluate whether this dose exerts the expected pharmacodynamic effects in myeloma cells before a larger phase II trial may be conducted. In light of new data supporting use of standard-dose azacitidine in myeloid neoplasia patients with kidney dysfunction(14) and GFR-adjusted lenalidomide for myeloma patients(15), amendment 7 extends the safety and preliminary efficacy evaluations to myeloma patients with GFR 30-59 ml/min (Cockroft-Gault). Lenalidomide will be used at a fixed dose of 10mg daily from day 1-21 every 28 days which yielded equal AUC concentrations in myeloma patients with GFR 30-49m/min as 25mg daily from day 1-21 every 28 days in patients with GFR \geq 80 ml/min in a recent study(15). Only two dose levels of azacitidine will be tested. Dose level "CKD 1" will use azacitidine at 40 mg/m² s.c. twice a week which has been found tolerable in patients with GFR \geq 60 ml/min; one of six patients developed a dose limiting toxicity, culture negative neutropenic fever at an absolute neutrophil count (ANC) nadir of 0.48K/mm³, with resolution the next day at an ANC of 0.89K/mm³ without G-CSF use. At the time of amendment 7, two patients with normal kidney function have completed the first cycle at dose level 5 (azacitidine 50mg/m² s.c. twice a week) without dose limiting toxicities. Six patients with GFR 30-59 ml/min will be treated at CKD 1 if dose limiting toxicities (DLTs) do not occur in more than one patient. If 2 of 3 or 2 of up to six patients develop DLTs at CKD1, subsequent patients will be treated at "CKD -1" (30mg/m² s.c. twice a week). Otherwise (no more than one patient with DLTs at CKD1), subsequent patients will receive azacitidine at 50mg/m² s.c. twice a week (= dose level CKD2). Lower or higher dose levels will not be tested. This modified dose escalation scheme increases safety by enrolling at least 6 patients per dose level and guarantees that the tolerability of twice a week azacitidine in patients with GFR 30-59 ml/min will be defined by enrolling maximally 12 additional patients. Omission of weekly azacitidine is based on the observation that clinical benefit response rates were more than twice as high with twice a week than with weekly azacitidine dosing (40% versus less than 15%) in patients with GFR > 60ml/min, an encouraging result taking into consideration that patients had received a median of 4.5 prior regimens, with myeloma refractory to previous lenalidomide in 88%, to previous proteasome inhibitors in 81%, and to both lenalidomide and proteasome inhibitors in 75%. Once the highest tolerated low dose for patients with reduced GFR (HTLD-CKD) has been defined, enrollment at this dose level may contribute to the 10 patient phase II extension. Before amendment 7 eighteen patients have started treatment, including two at dose level 5. Assuming up to 6 patients will be enrolled per dose level; the maximal number of enrolled patients will therefore increase from previously estimated 40 to 44 after amendment 7.

STUDY OBJECTIVES:

Primary:

- Define the highest tolerated low doses (HTLD and HTLD-CKD for GFR > 60 ml/min and 30-59ml/min, respectively) and safety of azacitidine given at low but increasing doses up to 50mg/m² twice a week concurrently with GFR-adjusted lenalidomide doses and low dose dexamethasone in patients with relapsed or refractory multiple myeloma.

Secondary:

- Response according to international response criteria (\geq PR) and clinical benefit response (\geq minor response according to adapted EBMT criteria), see under 7
- Correlate response with plasma activity of the azacitidine inactivating enzyme cytidine deaminase (CDA)
- Progression-free survival and overall survival
- Peripheral blood hematopoietic progenitor (CD34+) yield and time to neutrophil and platelet recovery in patients undergoing autologous stem cell transplantation
- Promoter demethylation and gene reactivation in myeloma cells and hematopoietic progenitors treated at the HTLD / HTLD-CKD level after one cycle of therapy
- Changes in global gene expression in myeloma cells treated at the HTLD / HTLD-CKD level after one cycle of therapy

STUDY DESIGN:

Two institutions phase I/II study, classical 3x3 design for patients with GFR \geq 60ml/min, modified 3x3 design for patients with GFR 30-59ml/min, with 10 additional patients treated at the highest tolerated low dose (HTLD / HTLD-CKD).

Patient population: Multiple myeloma, with relapsed or refractory disease (see under 5.3).

The Cockcroft-Gault formula will be used for all GFR estimations throughout this study (Appendix IV).

STUDY ENDPOINTS**Primary:**

- The highest tolerated low dose (HTLD and HTLD-CKD for GFR $>$ 60 ml/min and 30-59ml/min, respectively) of azacitidine in combination with GFR-adjusted lenalidomide will be defined as the dose level below which dose limiting toxicity (DLT) occurs during the first 28-day cycle in 2 out of three or out of up to 6 patients. If one out of the first 3 patients with GFR \geq 60ml/min develops DLT, up to three additional patients are treated at the same dose level. In patients with GFR 30-59ml/min each dose level will enroll 6 patients unless more than 1 patient develops DLT. The dose will not be escalated above 50mg/m² twice a week for reasons outlined under background and rationale of this synopsis. Any dose level evaluated as the possible HTLD / HTLD-CKD must include 6 patients assessed for DLT. DLT is defined in Section 5.1. Toxicity according to CTCAE v.4.0 will be assessed with weekly CBC w. Diff and CMP during the first 6 cycles, subsequently before each cycle, weekly history and physical during the first 28-day cycle, then before each cycle until cycle 12.

Secondary:

- Response will be determined monthly during the first 12 cycles and every two months thereafter with serum and 24hr urine protein electrophoresis, and as appropriate, supplemented by immunofixation, serum free light chain assay, and

bone marrow examination. Response before high dose melphalan and autologous stem cell transplant will also be confirmed by 2 separate blood and 24 hr urine tests between the last dose of combination therapy and the first dose of the mobilizing agent.

- Plasma from peripheral blood draws will be used to quantify the activity of CDA using an HPLC method (see under 5.5.3)
- Progression-free survival will be measured from study entry to progression as defined by international response criteria (see under 5.9.1) or death of any cause, whichever comes first.
- Overall survival will be measured from study entry to death from any cause.
- CD34+ cell yield will be calculated based on flow cytometry of mononuclear cells harvested following stem cell mobilization. Time to neutrophil ($\geq 1,000/\text{mm}^3$) and platelet ($\geq 100,000/\text{mm}^3$) recovery will be counted from the day of stem cell infusion (=day 0)
- Promoter demethylation and gene reactivation will be measured at least at the HTLD / HTLD-CKD level using the Illumina® HumanMethylation27 BeadChip array on CD138 purified and CD34 purified cells obtained from bone marrow aspirates within 7 days before treatment start and at the end of cycle #1. RNA will be harvested from the same cell populations to confirm reactivation of selected genes identified on the array. Since the HTLD / HTLD-CKD is identified retrospectively DNA and RNA will be isolated from purified cell populations from all bone marrow aspirations before and after cycle #1.
- The RNA harvested from myeloma cells before and after the first cycle of therapy at the HTLD / HTLD-CKD level will furthermore be used to identify changes in global gene expression using the Illumina® HT12 array.

STUDY DURATION: 24 months	TOTAL SAMPLE SIZE: up to 44 patients
----------------------------------	---

DRUG SUPPLIES:

For study participants, Celgene Corporation will provide lenalidomide at no charge through the RevAssist® program and azacitidine, also at no cost, via the Cleveland Clinic Taussig Cancer Center chemotherapy pharmacy or the pharmacy of the University Hospital Seidman Cancer Center.

DOSING REGIMEN(S):

Combination therapy (six 28-day cycles)

GFR $\geq 60\text{ml}/\text{min}$ (initial study cohort):

All dose levels (**during phase I portion of the study**):

- Lenalidomide 25mg p.o. d1-21 every 28 d
- Dexamethasone 40mg p.o. weekly

Azacitidine dose levels:

1. 30mg/ m^2 s.c. weekly
2. 40mg/ m^2 s.c. weekly

3. 30mg/m² s.c. twice a week
4. 40mg/m² s.c. twice a week
5. 50mg/m² s.c. twice a week

GFR 30-59 ml/min (amendment 7):

All dose levels (**during phase I portion of the study**):

- Lenalidomide 10mg p.o. d1-21 every 28 d
- Dexamethasone 40mg p.o. weekly

Azacitidine dose levels:

CKD -1. 30mg/m² s.c. twice a week

CKD 1. 40mg/m² s.c. twice a week

CKD 2. 50mg/m² s.c. twice a week

Maintenance therapy (

Lenalidomide at last tolerated dose until disease progression.

2 Schedule of Study Assessments *

Procedure	Screening ≤ 7 days before day 1, cycle 1, unless indicated otherwise	Cycle 1				Cycle 2		Cycle 3,4,5,6		Maintenance Monthly during first 6 cycles, then every 2 months	Discontinuation From Protocol Therapy	Follow-Up Phase Every 3 months for 3 years from entry
		Day 1	Day 8	Day 15	Day 22	Day 1	Weekly	Day 1	Weekly			
Record prior medications, treatments	X											
Record prior anti-cancer therapies	X											
Physical examination, vital signs, weight	X	X ¹	X	X	X	X		X		X	X	
ECOG performance status	X	X ¹	X	X	X	X		X		X	X	
Skeletal survey ²	X											
Bone marrow ³	X	X ¹				X						
ECG	X											
CBC with differential	X	X ¹	X	X	X	X	X	X	X	X	X	
Research blood sample (10mL EDTA, 10mL Heparin)	X	X	X	X	X	X		X				
Calculated creatinine clearance (by Cockcroft-Gault) ⁴	X	X ¹				X ⁴		X ⁴		X ⁴		
TSH ⁵	X ⁵	X ¹						X ⁵		X ⁵	X ⁵	
SPEP w m-spike, 24hr urine w m-spike, serum and urine immunofixation, serum quantitative immunoglobulins, serum free light chain assay, beta-2 microglobulin,	X	X ¹				X		X		X	X	
Complete metabolic panel	X	X ¹	X	X	X	X	X	X	X	X	X	
LDH, phosphorus, uric acid	X	X ¹										
Pregnancy testing ⁷	X ⁸	X ⁸	X ⁸	X ⁸	X ⁸	X ⁸		X ⁸		X ⁸	X ⁸	
Register patient into RevAssist® program ⁹	X ⁹											
Prescribe lenalidomide via RevAssist® ¹⁰		X ¹⁰				X ¹⁰		X ¹⁰		X ¹⁰		
Azacitidine administration		X ¹¹										
Dexamethasone prescription		X ¹²				X ¹²		X ¹²				
Response assessment ¹³						X		X		X	X	
Record adverse events ¹⁴		X	X	X	X			X		X	X ¹⁴	
Record concomitant therapies/procedures	X	X				X		X		X	X	
Obtain Follow-Up anti-cancer treatments												X
Obtain Follow-Up survival information												X

* Variations of ± 3 days of the scheduled visit are permitted.

If Physical examination, vital signs, weight and ECOG performance status were done within 7 days of Day 1, they do not need to be repeated at Study Day 1. An unscheduled visit can occur at any time during the study. Source must be maintained for these unscheduled visits. The date for the visit and any data generated must be recorded on the appropriate CRF. Source documents for these unscheduled visits must also be maintained.

Version: 07/16/2015

¹ If screening assessments were done within 7 days of Day 1, they do not need to be repeated at Study Day 1.

² A skeletal survey may be obtained up to 28 days before day 1, cycle 1. It will be repeated every 12 months or earlier if symptoms suggest bony progression.

³ With each bone marrow aspiration two 20mL samples, each containing 2mL of heparin, will be obtained for correlative studies in addition to routine clinical analyses as indicated. In addition to defined times, a bone marrow examination is required to confirm complete response and before high dose melphalan in patients who choose to undergo autologous stem cell transplantation. In patients who have measurable disease only in the bone marrow, the bone marrow biopsy and aspiration will be performed every three cycles (+/- 7 days) while on combination therapy and every six cycles (+/- 7 days) while on maintenance.

⁴ Calculated creatinine clearance (by Cockcroft-Gault) at baseline and before dosing at the start of each cycle until cycle 12, then every two cycles.

⁵ To include Thyroid Stimulating Hormone (TSH) at screening, at least every 16 weeks and at treatment discontinuation. To facilitate monitoring in the maintenance phase it is recommended to obtain TSH at day 1 of cycle 1, 4, 8, 12, 16, and so on. T3 and T4 levels may be assessed as clinically indicated.

⁶ If patients undergo stem cell transplantation before completion of six cycles, SPEP w m-spike, 24hr urine w m-spike, serum and urine immunofixation, and serum free light chain assay should be repeated before mobilization begins for confirmation of their pre-transplant response.

⁷ Pregnancy tests for females of childbearing potential. A female of childbearing potential (FCBP) is a sexually mature female who: 1) has not undergone a hysterectomy or bilateral oophorectomy; or 2) has not been naturally postmenopausal for at least 24 consecutive months (i.e., has had menses at any time in the preceding 24 consecutive months).

⁸ Pregnancy tests must occur within 10 – 14 days and again within 24 hours prior to prescribing lenalidomide (prescriptions must be filled within 7 days). FCBP with regular or no menstruation must have a pregnancy test weekly for the first 28 days and then every 28 days while on therapy (including breaks in therapy); at discontinuation of lenalidomide and at Day 28 post the last dose of lenalidomide. Females with irregular menstruation must have a pregnancy test weekly for the first 28 days and then every 14 days while on therapy (including breaks in therapy), at discontinuation of lenalidomide and at Day 14 and Day 28 post the last dose of lenalidomide (see Appendix I: Risks of Fetal Exposure, Pregnancy Testing Guidelines and Acceptable Birth Control Methods).

⁹ Lenalidomide must be prescribed through and in compliance with the RevAssist® program of Celgene Corporation. Prescriptions must be filled within 7 days.

¹⁰ Consideration should be given to prescribing lenalidomide 5 to 7 days in advance of Day 1 of each cycle to allow time for required patient and prescriber surveys, and drug shipment to patient. Any unused Revlimid® (lenalidomide) should be returned to the patient for disposition in accordance with the RevAssist® program. Lenalidomide will be taken by patients from day 1-21 of the 28 day cycle as outlined under 5.6.

¹¹ Azacitidine will be administered at the Taussig Cancer Institute and Case Medical Center as outlined under 5.6, with weekly dosing for dose levels 1 and 2, and twice-a-week administration for dose levels 3 to 5.

¹² Dexamethasone will be taken by patients weekly during cycle 1 to 6 as outlined under 5.6. At day one of each cycle it should be ascertained that patients have an active prescription.

¹³ Response according international uniform response criteria, outlined in section 7. If PD is suspected, response may be re-assessed through repeat of relevant lab tests at any time before the next planned assessment for confirmation.

¹⁴ An additional safety assessment will be done 28 days (+/- 2 days) following the last dose of protocol therapy.

3 Background and Rationale

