At least 3 patients will be treated in each dose level tested beginning with dose level 1. At any dose level, if none of the first 3 evaluable patients experience DLT in the first 28 day cycle, the next three patients will be treated at the next dose level. At any dose level, if DLT occurs in one out of three patients during the first 28 day cycle, up to 3 additional patients will be treated at the same dose level. If no DLT occurs in the additional 3 patients, subsequent 3 patients will be treated at the next dose level. Once DLT occurs in 2 patients treated at a given dose level no further patients will be accrued at this dose level but patients already on treatment will continue according to study protocol. If DLT occurs in 2 patients treated at a given dose level, the next lower dose level will be evaluated as the possible HTLD, and if only 3 patients had been enrolled at this dose level, an additional 3 patients will be enrolled to properly assess this dose level as the possible HTLD. The dose level at which DLT occurs in ≤ 1 out of 6 patients will be defined as the highest tolerated low dose (HTLD) and ten more patients will be accrued at this dose level. Six evaluable patients must be assessed for DLT at any dose level that is being considered as the HTLD. Patients experiencing a DLT during their first 28-day cycle may remain on study with appropriate dose reduction (5.7.3).

Dose escalation for patients with GFR 30-59ml/min:

Only two dose levels of azacitidine will be tested in combination with fixed dose lenalidomide. Starting with dose level “CKD 1” (DL CKD1), 3 patients will initially be enrolled and if no more than 1 experience DLT, 3 additional patients will be enrolled at the same dose level. If no more than 1 out of 6 patients treated at DL CKD1 develop DLT, subsequent patients will be enrolled at DL CKD2. Once 2 of 3 or 2 of up to 6 patients treated at a given dose level develop DLT, no further patients will be enrolled at that dose level. If this occurs at DL CKD1, subsequent patients will be enrolled at DL CKD-1. If it occurs at DL CKD2, DL CKD1 will be defined as HTLD-CKD. If 2 of 3 or 2 of up to 6 patients treated at DL CKD-1 develop DLT, the tested azacitidine / lenalidomide / dexamethasone regimen will be considered intolerable for patients with

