10.2.2 Safety

Data from all subjects who receive any protocol therapy will be included in the safety analyses. Subjects who entered the study and did not receive any protocol therapy and had this confirmed, will not be evaluated for safety. Adverse events will be recorded during the first 12 cycles, graded according to CTCAE v.4.0 whenever possible, and reported for the time points day 1 of cycle 2, 3, 6, 9, and 12 according to dose level treated. Additionally, worst overall toxicity will be reported at each publication.

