10.2.3 Response

The response rate (RR= sCR+CR+VGPR+PR) and clinical benefit response rate (CBRR=sCR+CR+VGPR+MR) will be analyzed for the entire study group, and for the 16-22 patients treated at the HTLD / HTLD-CKD according to whether patients had relapsed or refractory disease at study entry. All response categories require two consecutive assessments but the time a response is first reached will be used to calculate response rates after 6 and 12 cycles. Additionally, best response will be reported. If one or more patients on this trial elect to undergo stem cell transplantation, response before mobilization will be reported.

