10.3 Statistical Methodology

The Kaplan-Meier method will be used to report progression free survival and overall survival for patients treated at the HTLD / HTLD-CKD and for the entire study cohort but excluding patients who elect to undergo high dose chemotherapy and autologous stem cell transplantation. For statistical methods pertaining to pharmacodynamic analyses please see under correlative science (5.5).

11 Regulatory Considerations

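### Efficacy is planned only for the whole study group, which mixes weekly and twice-weekly azacitidine, and for a pooled HTLD / HTLD-CKD set, which mixes two renal cohorts; rows by schedule and dose level within cohort should be added

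*Combined protocol and SAP*

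**What the plan says.** **Schedules.** The footnote on azacitidine administration in section 2 gives the regimen "with weekly dosing for dose levels 1 and 2, and twice-a-week administration for dose levels 3 to 5". All three dose levels for GFR 30-59 ml/min in section 5.6.2.3 are twice weekly. Lenalidomide is 25 mg for GFR >=60 and 10 mg for GFR 30-59.

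**Observed difference.** Section 1 (Background and Rationale) states that "clinical benefit response rates were more than twice as high with twice a week than with weekly azacitidine dosing (40% versus less than 15" per cent). It gives this as the reason for testing no weekly level in the GFR 30-59 cohort. No numerators or denominators are given.

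**Efficacy sets.** Under section 10.2.3 the response rate and the clinical benefit response rate "will be analyzed for the entire study group, and for the 16-22 patients treated at the HTLD / HTLD-CKD", with a breakdown by relapsed or refractory disease. Under section 10.3 Kaplan-Meier PFS and OS are reported "for patients treated at the HTLD / HTLD-CKD and for the entire study cohort", leaving out transplanted patients.

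**Safety, by contrast.** Under section 10.2.2 adverse events are "reported for the time points day 1 of cycle 2, 3, 6, 9, and 12 according to dose level treated". No efficacy endpoint has a matching breakdown by dose level or schedule, and section 10 mentions no confidence intervals.

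**The concern.** The protocol treats azacitidine schedule as important enough to shape amendment 7, but the efficacy analysis takes no account of it. Patients on the schedule reported to do worse stay in the whole-group response rates and survival curves. That summary is therefore an average over two schedules, weighted by how many patients happened to enter each level.

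The other planned set avoids this mixture but has one of its own. It combines patients with GFR >=60 on lenalidomide 25 mg and patients with GFR 30-59 on 10 mg. Their azacitidine doses may differ, because HTLD and HTLD-CKD are determined separately.

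The trial is meant to give a first impression of efficacy before a larger phase II trial is considered. A reader planning that trial needs to know which regimen in which renal group a response rate belongs to. As written, section 10 does not guarantee this for any efficacy figure. Nor does it give a way to check the schedule contrast quoted in the synopsis.

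**Working it through.** **1. The plan's own totals reproduce.**
- Before amendment 7: 5 levels x 6 + 10 = 40, as stated.
- After it: (18 - 2) already treated below level 5 + 6 at level 5 + 12 with GFR 30-59 + 10 extension = 44, as stated.
- HTLD / HTLD-CKD set: 6 + 10 = 16, or 6 + 6 + 10 = 22, matching the 16-22 in section 10.2.3.

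**2. How many weekly patients are there?** The documents do not say, so this is inferred.
- Section 1: "Before amendment 7 eighteen patients have started treatment, including two at dose level 5".
- Section 1, on 40 mg/m2 twice weekly (level 4): "one of six patients developed a dose limiting toxicity".
- Section 5.1: "At least 3 patients will be treated in each dose level tested beginning with dose level 1".

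Level 5 takes 2, level 4 at least 6, and levels 1, 2 and 3 at least 3 each: 2 + 6 + 9 = 17 of 18. One patient is unplaced. Weekly patients (levels 1-2) are therefore 6 or 7, which is 13.6-15.9% of 44.

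**3. Effect on the whole-group clinical benefit rate.** Assume the stated rates persist: 40% twice weekly, and anything from 0% to 15% weekly.

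Pooled rate = [w x p_weekly + (N - w) x 0.40] / N

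| N | w | p_weekly | Pooled | Loss against 40% |
|---|---|---|---|---|
| 44 | 7 | 0% | 33.6% | 6.4 points |
| 44 | 7 | 15% | 36.0% | 4.0 points |
| 44 | 6 | 0% | 34.5% | 5.5 points |
| 44 | 6 | 15% | 36.6% | 3.4 points |
| 28 (assumed early stop) | 7 | 0% | 30.0% | 10.0 points |
| 28 (assumed early stop) | 6 | 15% | 34.6% | 5.4 points |

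The documents give no rates by schedule for response of at least PR, PFS or OS, so no size can be put on those.

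**4. Does the HTLD / HTLD-CKD set contain weekly patients?** No. Level 4 had already met the rule of at most 1 DLT in 6, so the HTLD is level 4 or level 5. Every GFR 30-59 level is twice weekly. What the set does mix is lenalidomide 25 mg with 10 mg, and possibly two azacitidine levels.

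**5. What would added rows look like?** Twice-weekly patients with GFR >=60: level 3 (3-4) + level 4 (6) + level 5 (6) = 15-16, plus 0-10 extension patients, so 15-26. GFR 30-59: at most 12 plus 0-10, so up to 22. Exact (Clopper-Pearson) 95% intervals near 40%:
- 6/15: 16-68%
- 10/26: 20-59%
- 5/12: 15-72%

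The planned pooled HTLD / HTLD-CKD set gives 15-65% at 6/16 and 21-64% at 9/22. Splitting does not narrow the intervals.

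**6. Can the 40% versus under 15% be tested?** No, because the counts are not given. The prior-refractoriness percentages in the same sentence (88%, 81%, 75%) fit 14, 13 and 12 of 16, whereas 18 patients had started treatment. So even the denominator is unclear.

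**The case against.** The strongest reply is that the plan already covers the dose that matters. The same sentences that name the whole group also plan response, PFS and OS at the HTLD / HTLD-CKD. A reader might infer that every planned efficacy result is contaminated by weekly patients. The documents do not support that, because step 4 shows that this set holds none.

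A second reply is that the loss is small. At full enrolment 3.4-6.4 points lies well inside any interval this trial can produce. Efficacy is secondary, with no hypothesis or power, and comparing schedules is not an objective. That is also fair, and it keeps the point at the level of reporting.

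A third is that the HTLD set wastes twice-weekly patients at other levels, or conversely that a finer split would help precision. Neither reading holds. Leaving out other levels is what a dose-specific estimate requires, and step 5 shows that rows by GFR cohort are no tighter than the planned set. Pooling levels 3-5 would also mix three starting doses, and section 5.7.2 lets non-responders move to higher azacitidine doses. Rows should therefore be read as results by assigned starting level.

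What stands is that the whole-group result mixes schedules reported to differ, the HTLD / HTLD-CKD result mixes two renal cohorts, and efficacy lacks the dose-level breakdown that safety has.

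**Conclusion.** The point holds as a reporting gap of modest size. The whole-group clinical benefit rate would read about 34-37% where the twice-weekly rate is 40%. This assumes 6-7 weekly patients among 44 and that the rates quoted in section 1 persist; with an assumed 28 patients it would be about 30-35%. The HTLD / HTLD-CKD result is free of weekly patients and should remain the main efficacy result, but it is not sure to describe one regimen because it pools cohorts on different lenalidomide doses.

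A reader might go further and conclude that the schedule difference is real, or that it is only chance. The documents support neither, since the counts behind the percentages are not stated. The contrast should be treated as exploratory.

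**What to change.** In sections 10.2.3 and 10.3:
- Keep both planned summaries. Label the whole-group one descriptive and name the HTLD / HTLD-CKD set as the main efficacy set.
- Add RR and CBRR with exact 95% confidence intervals by azacitidine schedule and assigned dose level within GFR cohort, in line with section 10.2.2.
- Show the HTLD and HTLD-CKD cohorts separately as well as pooled.
- Give Kaplan-Meier PFS and OS by schedule within GFR cohort as descriptive output.

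In section 1, state the numerators and denominators behind the 40% and under-15% figures and call the contrast exploratory.

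While 10.2.3 is open, reconcile its CBRR formula with section 4.1.2. The formula sums sCR, CR, VGPR and MR and omits PR, whereas the objective counts every response of at least MR. Until that is settled, a CBRR from this plan cannot be compared with the 40%.

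The cost is wording and extra table rows, with no new data. The downside is small groups with wide intervals, such as 16-68% at 6/15 and 15-72% at 5/12, and a weekly survival curve on 6 or 7 patients at most.
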